2. SUMMARY

| | |
|----------------------------------------------|----------------------------------------------------------------------------------------------------------------------------------------------------------------------------------------------------------------------------------------------------------------------------------------------------------------------------------------------------------------------------------------------------------------------------------------------------------------------------------------------------------------------------------------------------------------------------------------------------------------------------------------------------------------------------------------------------------------------------------------------|
| Study Objective | To compare the 1-, 3-, and 5-year outcomes of a second aqueous shunt (SAS) to Transscleral Diode Laser Cyclophotocoagulation (TLC) in eyes with uncontrolled glaucoma with a single existing aqueous tube shunt implant. |
| Study Endpoint (Failure) | 
 1. Intraocular pressure (IOP) 
 a. > 18 mmHg on maximum tolerated topical IOP-lowering medications, or b. reduced by < 20% on maximum tolerated topical IOP-lowering medications from medicated preoperative IOP, or c. ≤ 5 mmHg without glaucoma medications on IOP confirmation visit(s), 6 months after initial study intervention; or 2. Additional reoperation for glaucoma (enhancement procedures allowed in the first 4 months); or 3. Addition of an oral carbonic anhydrase inhibitor (CAI) for the study eye on or after the 6-month visit; or 4. No light perception (NLP) |
| Study Population | 18 to 85 years of age with uncontrolled glaucoma on maximum tolerated topical therapy with a single existing tube shunt implant |
| Study Design | Prospective, multicenter, randomized, masked, parallel group |
| Treatment Groups | 
 1. Second Aqueous Shunt Implant (SAS) 2. Transscleral Diode Laser Cyclophotocoagulation (TLC) |
| Duration of Participant Participation | 5 Years |
| Number of Study Visits | 10 – 13 visits |
| # of Evaluable Participants | 91 in each group (182 total) |
| Anticipated Maximum # of Participants | 280, allowing for a 35% dropout |
| Recruitment Period | 1 year |
| Study Centers | Up to 70 centers |
| Site Funding Available | No |
| IRB Submission | Site's responsibility (submission, questions, fees) |

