7.2. Randomization Scheme

An adaptive block randomization scheme will be implemented with a block size of 4 and balancing between NVG and non-NVG strata within each site.

Upon completion of the Screening/Baseline visit, the study eye will be randomly assigned to one of the 2 treatment groups: SAS or TLC within each stratum (NVG vs non-NVG) and each site based on the computer generated assignment.

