7.3. Masking

Since intraocular pressure (IOP) is one of the most important measurements for determining treatment success or failure, every effort will be made to obtain unbiased measurements through a masking procedure. IOP will be performed by two study personnel, an operator and a masked reader. Masking procedures are detailed in section 10.3.7.

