8. RECRUITMENT PROCEDURE

Recruitment is open for competitive enrollment. The Investigators and/or study staff will enroll qualified participants into the study. After reviewing and signing the informed consent form, a study number will be assigned to the participant in a sequential manner by site identification (assigned by REDCap) followed by participant number. All potential participants will undergo an initial screening examination (Table 2) in order to determine study eligibility.

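### One stated block size of 4 within each site and stratum lets sites deduce some assignments in advance: an expected third in completed blocks, about 14–31% trial-wide depending on site numbers

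*Combined protocol and SAP*

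**What the plan says.** Section 7.2 describes an adaptive block scheme "with a block size of 4 and balancing between NVG and non-NVG strata within each site". Assignment is to "SAS or TLC within each stratum (NVG vs non-NVG) and each site based on the computer generated assignment". No other block size appears, and nothing says that the size is withheld from sites. The word adaptive is not explained.

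Section 2 describes the trial as "Prospective, multicenter, randomized, masked, parallel group". Section 7.3 covers IOP measurement only: "IOP will be performed by two study personnel, an operator and a masked reader". Section 10.3.7 adds that the reader is masked to treatment. No one else is described as masked to treatment.

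Under Section 8.1, REDCap gives the site the assignment once screening data have been entered and eligibility is confirmed. Section 6.2 includes a catch-all exclusion resting on the investigator's opinion, and another for too little conjunctiva to cover a shunt.

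Section 2 allows up to 70 centers and a maximum of 280 participants. Section 8 says: "Recruitment is open for competitive enrollment". No cap per site is given.

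**The concern.** Central release hides the allocation list, but it does not hide what a site has already seen. One arm receives an implant and the other a laser session, so treating staff know every earlier assignment at their site. If they also know that each run of four eyes in a stratum holds two of each treatment, the end of the run can be deduced.

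Someone who knows or strongly suspects the next assignment can enroll, defer or exclude a patient accordingly, using the discretion that Section 6.2 leaves. The groups could then differ at baseline. The Fisher and log-rank comparisons in Section 16.2 do not address this, and the Cox models there can adjust only for factors that were recorded and included. Masking the IOP reader does not help, because the bias arises before treatment.

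**Working it through.** **The plan's own figures.** The documents give none for predictability. The sample size, which this point does not depend on, reproduces: with 50% versus 30%, two-sided 5%, 80% power and unpooled variance, n = (1.960 + 0.842)² × (0.25 + 0.21) / 0.04 = 90.3, so 91 per group. Then 182 / 0.65 = 280.

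**Inputs.** Block size 4, two arms, blocks within site and NVG stratum (Section 7.2). A 1:1 ratio, implied by 91 per group (Section 2). At most 280 participants and up to 70 sites (Section 2). The NVG share and the spread of enrollment across sites are not given; I assume 10–30% NVG, with site sizes either equal or uneven (weights drawn from an exponential distribution).

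**Completed block of 4.** There are six equally likely sequences. An assignment is certain when one arm has used both of its places.

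| Position | Probability already certain | Probability best guess is right |
|---|---|---|
| 1 | 0 | 1/2 |
| 2 | 0 | 2/3 |
| 3 | 1/3 | 1/3 × 1 + 2/3 × 1/2 = 2/3 |
| 4 | 1 | 1 |

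- Expected certain share: (0 + 0 + 1/3 + 1) / 4 = 33.3%. In a given block it is 25% (four of the six sequences) or 50% (two of six).
- Best guess right: (0.500 + 0.667 + 0.667 + 1) / 4 = 70.8%, against 50% by chance.

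**Incomplete blocks.** A cell with 3 participants has (1/3) / 3 = 11.1% certain and (0.500 + 0.667 + 0.667) / 3 = 61.1% guessed. A cell with 2 has none certain and (0.500 + 0.667) / 2 = 58.3% guessed. With 70 sites the mean cell holds 280 / (70 × 2) = 2 participants, but cells vary around that mean.

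**Trial-wide share.** Distributing 280 participants over sites and strata by simulation, and applying the position probabilities above to each cell, gives:

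| Sites | Certain share | Assignments of 280 |
|---|---|---|
| 10 | 30–31% | 85–86 |
| 20 | 27–29% | 77–80 |
| 40 | 21–25% | 60–71 |
| 70 | 14–22% | 40–61 |

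**Random blocks of 4 and 6.** Assume that sites know the two possible sizes, equally likely, but not the size of each block. In a cell of 4, an assignment is certain only if the first three match, which reveals a block of 6: 1/2 × 2 × (3/6 × 2/5 × 1/4) = 5% at position 4, so 5% / 4 = about 1% of the cell. Carrying the same reasoning to larger cells:

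| Cell size | Certain: fixed 4 → mixed 4/6 | Best guess right: fixed 4 → mixed 4/6 |
|---|---|---|
| 4 | 33% → 1% | 71% → 65% |
| 6 | 22% → 7.5% | 67% → 67% |
| 8 | 33% → 6% | 71% → 67% |
| 12 | 33% → 6% | 71% → 68% |

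**The case against.** The strongest reply is that the exposure is limited. REDCap conceals the list until eligibility is confirmed. Many entry criteria are objective: IOP above 18 mmHg, acuity of hand motion or better, a single existing shunt, no earlier cyclodestruction. Section 7.5 plans for as many sites as possible, which makes cells small, and a cell of one or two has no certain assignment. Exploiting the blocks would require a site to track its sequence by stratum and act on it. Section 16.1 also provides for monitoring balance in prognostic factors.

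Much of this stands, and it limits the size of the problem. It does not remove it. Seventy sites is a ceiling, enrollment is competitive, and even at 70 sites an estimated 40–61 assignments are certain in advance. Monitoring balance can reveal differences only in factors that are measured.

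A second reply is that adaptive may mean something other than plain permuted blocks, in which case the one-third figure might not apply. That is fair, and only the sponsor can settle it.

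**Conclusion.** The point holds as a moderate, avoidable weakness. The expected certain share is 33% in completed blocks. Trial-wide it is about 14–22% with 70 sites, rising to 27–31% with 10–20. These figures rest on permuted 1:1 blocks of 4, on sites keeping track of their own history, and, for the trial-wide range, on the assumed NVG share and site sizes.

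A reader might infer four stronger things that the documents do not support:

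- That the trial is unmasked. It is labelled masked and the IOP reader is masked; the accurate statement is that treating staff know the assignments, which cannot be avoided when an implant is compared with laser.
- That a third of all assignments are foreseeable. That is the expectation for completed blocks, and it is not a strict maximum either, since one block can reach half.
- That steering will occur. The plan permits it; nothing shows that it is likely.
- That mixing block sizes abolishes the problem. It removes most of the certainty but only a little of the guessing advantage.

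**What to change.** For blocks not yet started:

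1. Generate the central REDCap list with randomly varying block sizes, for example 4 and 6, keeping the same site and NVG strata.
2. Move the block sizes from Section 7.2 to a document that sites do not hold.
3. State in Section 7.2 what adaptive means, or delete the word.

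If sites still know the possible sizes, expect about 1% certain in cells of 4 and 6–8% in cells of 6–12, with best-guess accuracy of about 65–68% and no gain in guessing at cell size 6. Withholding the sizes lowers certainty further.

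The cost is a new allocation list and a worst imbalance within a site-stratum cell of 3 instead of 2 (half of the largest block). Sample size, strata and study procedures stay as they are.

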7.3. Masking

Since intraocular pressure (IOP) is one of the most important measurements for determining treatment success or failure, every effort will be made to obtain unbiased measurements through a masking procedure. IOP will be performed by two study personnel, an operator and a masked reader. Masking procedures are detailed in section 10.3.7.

7.4. Sample Size Calculations

The definition of success/failure in this study is similar to the Ahmed versus Baerveldt Comparison (ABC) study.³ In the ABC study, the 1- and 5-year failure rate for the primary Baerveldt tube shunt group was 14% and 34%, respectively. Anticipated failure rate for the SAS group is 50% more than the primary tube shunt (~21%=14% x1.5 for 1 year, and 50% = 34%x1.5 for 5 years). Setting the power at 80% and alpha at 5%, a sample size of **91** participants in each group (182 total) would allow us to detect a difference of 20% or more reduction in cumulative incidence of failures in the TLC group from an anticipated 50% failure at 5 years in the SAS group (i.e. <30% in TLC vs 50% in SAS).

The retention rate in the ABC study was 65% at the 5-year visit. A total of **280** participants would allow for a 35% dropout rate (or deaths) during the 5-year study period.

7.5. Recruitment period

The intent of this study is to answer a question that is desperately needed within the glaucoma community. In order to have the question answered in a timely manner, the study plans to involve as many sites as possible from the AGS membership and thereby shorten the recruitment period to one year.

7.6. Investigator/Site Selection

Study investigator/site selection will be based on the cumulative number of at least 10 TLCs and 20 ASs (at least 5 of which being inferonasal tube shunts) implanted by an investigator. Additionally, sites must have the necessary staffing and resources to conduct this study.

8. RECRUITMENT PROCEDURE

Recruitment is open for competitive enrollment. The Investigators and/or study staff will enroll qualified participants into the study. After reviewing and signing the informed consent form, a study number will be assigned to the participant in a sequential manner by site identification (assigned by REDCap) followed by participant number. All potential participants will undergo an initial screening examination (Table 2) in order to determine study eligibility.

8.1. Randomization Procedure

Upon completion of the Screening/Baseline visit, sites will enter the Screening/Baseline visit data into the research electronic data capture (REDCap) system to confirm eligibility. Once eligibility of the participant is confirmed, the REDCap system will provide the participant

randomization assignment, SAS or TLC. The participant should be treated within **45** days of the Screening/Baseline visit or the Screening/Baseline visit must be performed again.

9. SURGICAL PROCEDURES

9.1. Second Aqueous Shunt (SAS)

9.1.1. Anesthesia

Anesthesia is at the discretion of the surgeon. The site will record accordingly.

9.1.2. Placement of Aqueous Shunt

Either a *Baerveldt* Glaucoma Implant 350-mm² BG101-350 or an *Ahmed* Model FP7 Flexible Plate must be used for all participants unless there is insufficient space, in which case a Baerveldt Glaucoma Implant 250-mm² BG103-250 may be used. The implant's preferred location is approximately 180 degrees from the existing initial plate. Tube insertion through the anterior chamber, sulcus, or pars plana is acceptable and will be documented. The site will record the model selected, the quadrant in which it was implanted, the clock hour in which the tube was inserted, and complications, if any.

Implants may not be modified in anyway (e.g. trimming the plate).

9.1.3. Occlusion of Tube (Baerveldt only)

The Baerveldt Glaucoma Implant must be completely occluded in all cases. The method of occlusion is left to the discretion of the surgeon. Occlusion must be tested ensuring there is no flow through the tube or around the sclerostomy. Fenestration of the tube or wick placement is allowed. The site will document the occlusion method used by the surgeon in each case.

9.1.4. Tube Coverage

The type and use of patch graft used to cover the tube is at the discretion of the surgeon. The site will record if a graft is used and the type in each case.

9.1.5. Intraoperative Medications

The use of mitomycin-C, 5-fluorouracil or anti-vascular endothelial growth factor (VEGF) agents are not allowed at the time of aqueous shunt implantation. Other intraocular medications are allowed.

9.1.6. Concurrent Procedures

Except for tectonic aqueous shunt revisions, concurrent procedures are not allowed at the time of aqueous shunt implantation.

9.1.7. Postoperative Medications

Postoperative medication regimen is at the surgeon's discretion. The site will record accordingly.

9.2. Transscleral Diode Laser Cyclophotocoagulation (TLC)

9.2.1. Anesthesia

Anesthesia is at the discretion of the surgeon. The site will record accordingly.

9.2.2. Laser Settings

Recommended settings are 2000 mW for 2 seconds, 1850 mW for 3 seconds, or 1750 mW for 4 seconds duration, titrating the energy up or down just below where a pop is heard. The site will record starting energy, duration, end energy, and total energy used.

9.2.3. Laser Procedure

Four to eight spots should be used per quadrant for a total of up to 16 spots per 180 degrees (or 2 quadrants). Up to 180 degrees (or 2 quadrants) should be lasered during the initial treatment session. Selection of quadrants to be treated is at the investigator's discretion. The site will record the total number of treatment spots performed. If available, the site will record, the number of prior uses of the G probe.

9.2.4. Concurrent Procedures

Except for tectonic aqueous shunt revisions, concurrent procedures are not allowed at the time of TLC.

9.2.5. Postoperative Medications

Type of postoperative medications is at the surgeon's discretion. The site will record accordingly.

9.3. Enhancement Procedure

The following qualified enhancement procedure must be completed within 4 months of the "initial study treatment visit/Day 0)".

9.3.1. Second Aqueous Shunt

Needling of the bleb over the tube shunt plate is allowed within the first 4 months following the initial study treatment. Manual or laser opening of the ligature or obturator removal is *not* considered an enhancement.

9.3.2. Transscleral Diode Cyclophotocoagulation

One additional TLC session (up to 2 additional quadrants, not to retreat previously treated quadrants) may be performed in the first 4 months following the initial study treatment.

10. SCHEDULED STUDY VISITS AND ASSESSMENTS

10.1. Study Visit Schedule

10.1.1. Screening/Baseline Visit

After reviewing and signing the informed consent form, all potential participants will undergo a screening examination in order to determine study eligibility, establish baseline ocular characteristics, and assignment to SAS or TLC based on the computer-generated assignment. If available, the mean deviation (MD) from the most recent visual field, prior to or during the Screening/Baseline visit will be collected to further characterize the stage of disease within the study population.

10.1.2. Scheduled Follow-up Visits

Every attempt should be made to conduct each follow-up evaluation within the visit windows (Table 1): Week 1 (-3 days to +14 days), Month 1 (-8 days to +29 days), Month 3 (± 1 month), Month 6 (-2 to +3 months), Month 12 (-3 to +6 months), Year 2 (± 6 months), Year 3 (-6 months to +1 year), and Year 5 (-1 year to +6 months). Evaluations conducted outside the visit window will be considered protocol deviations.

Table 1. Time Windows for Scheduled Follow-Up Visits (number of days after initial study surgery)

| Follow-Up Visit | Ideal Time | Preferred Time Window | Acceptable Time Window |
|------------------------|-------------------|------------------------------|-------------------------------|
| Week 1 | 7 days | 6-8 days | 4-21 days |
| Month 1 | 30 days | 23-37 days | 22-59 days |
| Month 3 | 90 days | 76-104 days | 60-120 days |
| Month 6 | 182 days | 161-203 days | 121-273 days |
| Month 12 | 365 days | 305-425 days | 274-547 days |
| Year 2 | 730 days | 670-790 days | 548-912 days |
| Year 3 | 1095 days | 1005-1185 days | 913-1460 days |
| Year 5 | 1825 days | 1735-1915 days | 1461-2007 days |

10.1.3. Post-Enhancement Scheduled Follow-up Visits

If an enhancement is performed after the Month 3 Study visit, the participant should be scheduled to return for a follow-up visit 1 month from the enhancement and then resume the normal study schedule. If an enhancement occurs prior to the Month 3 Study visit, the Enhancement 1 Month Study Visit is not required.

10.1.4. IOP Confirmation Visit

If a participant's study eye meets the IOP failure criteria, either at a study visit or a nonstudy visit, a confirmation visit will be scheduled at approximately the same time of day within six weeks during the first year postoperatively and within 3 months after 1 year postoperative visits. Unless an emergent intervention is required, confirmation visits should occur when:

1. IOP is >18 mm Hg on maximum tolerated topical IOP-lowering medications 6 months after initial study intervention, or
2. IOP reduction is < 20% on maximum tolerated topical IOP-lowering medications from medicated preoperative IOP 6 months after initial study procedure, or
3. IOP is ≤ 5 mm Hg without IOP-lowering medications 6 months after initial study procedure

10.2. Scheduled Assessments

Table 2 outlines the schedule of assessments at each visit throughout the study period. Data from the study visits must be entered into the REDCap system within 5 business days of the exam.

Table 2: Schedule of Assessments

| Assessment | Screening / Baseline | Surgery – Day 0 | Week 1 | Month 1 | Month 3 | Enhancement Procedure | Enhancement Month 1 | Month 6 | Month 12 | Year 2 | Year 3 | Year 5 / Exit | Confirmation Visit*** |
|------------------------------------|----------------------|-----------------|--------|---------|---------|-----------------------|---------------------|---------|----------|--------|--------|---------------|-----------------------|
| Informed Consent | X | | | | | | | | | | | | |
| Demographics | X | | | | | | | | | | | | |
| Medical / Ophthalmic History | X | | | | | | | | | | | | |
| Historical VF MD* | SE | | | | | | | | | | | | |
| Concomitant Medications | OU | | OU | OU | OU | OU | OU | OU | OU | OU | OU | OU | OU |
| Inclusion/Exclusion Criteria | X | | | | | | | | | | | | |
| Visual Acuity | OU | | SE | SE | SE | | SE | SE | SE | SE | SE | SE | |
| Binocular Diplopia | X | | | | X | | | X | X | X | X | X | |
| External Ocular Examination | OU | | | OU | OU | | | | OU | | | | |
| Specular Microscopy (CCT and CD)** | SE | | | | | | | | SE | | | SE | |
| Biomicroscopy | SE | | SE | SE | SE | | SE | SE | SE | SE | SE | SE | |
| Intraocular Pressure | OU | | SE | SE | SE | | SE | SE | SE | SE | SE | SE | SE |
| Ultrasonic Pachymetry | OU | | | | | | | | SE | | | SE | |
| Ophthalmoscopy | SE | | | | | | | | SE | | | SE | |
| OCT (macula) | SE | | | | | | | | SE | | | | |
| Procedure | | SE | | | | SE | | | | | | | |
| VFQ-25 | X | | | | | | | | X | | X | X | |
| Randomization | X | | | | | | | | | | | | |
| Pain Scale | | | X | X | | | | | | | | | |
| Adverse Events | X | X | X | X | X | X | X | X | X | X | X | X | X |

Perform assessment, not eye specific (X), study eye only (SE), both eyes (OU)

* The mean deviation from the participants last visual field (if available) prior to enrollment will be recorded to further describe the stage of disease in the study population.

**Specular microscopy (SM) will be performed at sites where SM is available

***Confirmation visits will occur prior to the conduct of any surgical intervention in the study eye when IOP is believed to have met endpoint (failure).

10.3. Assessments

The same examiner should perform the same assessments for each participant whenever feasible throughout the study.

10.3.1. Ocular Medications

All IOP-lowering medications that the participant is taking at the time of the Screening/Baseline visit and for the duration of the study will be recorded. Concomitant medications will be captured by class of medication.

No investigational drugs may be used during the study and participants may not participate in any other medical or device study during the course of this investigation.

10.3.2. Visual Acuity

Visual Acuity testing should precede IOP measurement, the administration of eye drops to dilate or anesthetize the eye, or any examination requiring contact with the eye. A decrease in visual acuity of *more than two lines* should be reported as an adverse event (or the cause of the decrease in visual acuity).

Manifest refraction must be performed prior to Best-Corrected Visual Acuity (BCVA) at all visits assessing vision except Week 1. Pinhole visual acuity may be used for the Week 1 postoperative visit.

The Snellen visual acuity chart should be used to measure BCVA. The participant's visual acuity will be recorded as the last line read on which two or fewer letters were missed. If the participant cannot read the largest letter on the chart, the examiner should perform the following tests:

Count Fingers: The examiner should hold his/her fingers in front of the participant's eye in good light and the vision is recorded as the furthest distance that the fingers can be counted, CF (feet).

Hand Motion: If the participant cannot see or count fingers, the examiner should wave a hand in front of the eye at a distance of two feet. If movements of the hand are seen by the participant, then the vision is recorded as HM.

Light Perception: If visual acuity is so poor that the participant cannot read any of the letters and fails counting fingers and hand motion test, light perception needs to be tested with the indirect ophthalmoscope as the light source. Room lighting should remain at the level of normal visual acuity testing. The participant should close the opposite eye and cover it with the *palm* of their hand. The indirect ophthalmoscope light should be in

focus at 1 meter (3 feet) with the rheostat set at maximum voltage. From a distance of 3 feet, the beam should be directed in and out of the eye at least 4 times, and the participant should be asked to respond when he or she sees the light. If the examiner is convinced that the participant sees the light, vision should be recorded as LP. If the examiner is convinced that the participant does not see the light, vision should be recorded as NLP.

